### 9.6.2 Statistical Methods for Efficacy Analysis

- Objective Response (OR)

The point estimate and exact 95% Clopper-Pearson CI for response rates will be provided. Participants with missing data will be considered non-responders. This analysis will also be performed based on data pooled across all participants who eventually receive 65 mg.

- Duration of Response (DOR)

If the number of participants who achieve an objective response permits, DOR will be summarized descriptively using Kaplan-Meier medians and quartiles. Only the subset of participants who achieve an objective response will be included in this analysis. Details will be documented in sSAP as appropriate.

A summary of the primary analysis strategy for the key efficacy endpoints is provided in [Table 11](#).

Table 11 Analysis Strategy for Key Efficacy Variables

Endpoint/Variable	Statistical Method	Analysis Population	Missing Data Approach
OR per disease-specific criteria † by investigator	Summary statistics with 95% CI using Exact method based on binomial distribution	APaT	Participants with missing data are considered nonresponders
DOR per disease-specific criteria † by investigator	Summary statistics using Kaplan-Meier method	Responders in APaT population	Details will be documented in sSAP
Abbreviations: APaT=all-participants-as-treated; CI=confidence interval; DOR=duration of response; OR=objective response; sSAP=supplemental statistical analysis plan. † See Section 8.2.1			

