## 4 STUDY DESIGN

### 4.1 Overall Design

This is a Phase 1, open-label, multisite, dose escalation study of nemtabrutinib in Japanese participants with Mature B-cell neoplasms who have failed or are intolerant to previous treatment. This study will evaluate the safety, tolerability, PK and preliminary efficacy of nemtabrutinib.

The study design is shown in [Figure 1](#). This study will enroll patients according to a modified toxicity probability interval (mTPI) design and perform dose escalation of nemtabrutinib at each predetermined dose levels (45 mg QD or 65 mg QD). To evaluate the DLT, participants will be enrolled to one dose level at the same time. Study medication will be administered at the following dose levels;

- Dose level 1 (DL1): 45 mg QD
- Dose level 2 (DL2): 65 mg QD

Details of DLT assessment schedules and rules are described in Section 4.3.2. The definition of DLTs is provided in Section 4.3.1. In principle, during DLT assessment period, participants will be hospitalized.

AEs will be evaluated by the investigator, according to criteria outlined in the NCI-CTCAE, version 5.0, to establish the safety and tolerability of nemtabrutinib monotherapy per the primary objective of this study.

Secondary objectives of this study are to evaluate PK following administration of nemtabrutinib and to evaluate ORR and DOR assessed by the investigator using assessment criteria of each disease as a preliminary efficacy evaluation. PFS and OS assessed by the investigator using assessment criteria of each disease are evaluated as tertiary/exploratory objectives.

Treatment response assessments may include computed tomography (CT)/magnetic resonance imaging (MRI) and/or positron emission tomography (PET) imaging, and laboratory assessments. Treatment response assessments will be performed during screening, every 12 weeks ( $\pm 7$  days), and every 24 weeks ( $\pm 7$  days) after 4 years and should follow calendar days from C1D1.

Patients will continue taking nemtabrutinib 45 mg or 65 mg QD until unacceptable toxicity, disease progression, or another discontinuation criterion described in Section 7.1 is met.

In or after cycle 4, participants receiving 45 mg of nemtabrutinib may be escalated to the 65 mg if the tolerability is confirmed at the 65 mg of nemtabrutinib and at the discretion of the investigator after discussion with the participant, upon the consultation with the sponsor.

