## 6.6 Dose Modification (Escalation/Titration/Other)

Nemtabrutinib – any treatment interruption more than 21 consecutive days needs to be discussed with the sponsor.

In or after cycle 4, participants receiving 45 mg of nemtabrutinib may be escalated to the higher dose if the tolerability is confirmed at the 65 mg of nemtabrutinib and at the discretion of the investigator after discussion with the participant, upon the consultation with sponsor.

If the escalation is permitted, the higher dose can be utilized from the Day 1 of next cycle based on the approved date.

The participants who receive the higher dose of nemtabrutinib should perform site visit / telephone contact after 14 ( $\pm 3$ ) days and 28 ( $\pm 3$ ) days from the first dose of the escalated dose to assess adverse event. Refer to Section 1.3 for the detailed schedule.

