### **8.2.2 Tumor Response Assessments**

Throughout this section, the term 'scan' refers to any medical imaging data used to assess tumor burden and may include cross-sectional imaging (such as CT or MRI), medical photography, or other methods as specified in this protocol.

In addition to survival, efficacy will be assessed based on imaging evaluation of changes in tumor burden over time, until the participant is discontinued from the study or goes into survival follow-up. Disease response assessments may use CT/MRI and/or PET imaging, laboratory studies, and physical examination. The same imaging technique should be used in

a participant throughout the study to optimize the reproducibility of the assessment of existing and new tumor burden and improve the accuracy of the response assessment based on imaging. Note: for the purposes of assessing tumor imaging, the term “investigator” refers to the local investigator at the site and/or the radiological reviewer at the site or at an offsite facility. Other imaging modalities that may be collected and included in response assessment include bone scans and dedicated brain imaging. Other types of medical imaging (such as ultrasound) should not be included in response assessment.

Initial tumor imaging at Screening must be performed within 28 days prior to the date of allocation. Any imaging obtained after Cycle 1 Day 1 of treatment cannot be included in the screening assessment. The site study team must review screening images to confirm the participant with other than CLL/SLL has measurable disease.

Tumor imaging performed as part of routine clinical management is acceptable for use as screening tumor imaging if it is of diagnostic quality and performed within 28 days prior to the date of allocation.

The first on-study imaging assessment and tumor response assessment should be performed at 12 weeks ( $84 \pm 7$  days) from the date of Cycle 1 Day 1. Subsequent tumor imaging and tumor response assessment should be performed every 12 weeks ( $84 \pm 7$  days) or more frequently if clinically indicated. Imaging and tumor response assessment frequency can be decreased to every 24 weeks ( $168 \pm 7$  days) starting the fourth year on study, regardless of dose interruption or delays.

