### 9.4.2 Efficacy Endpoints

- Objective Response (OR)

OR is defined as participants who achieve at least a PR, per disease-specific criteria (see Section 8.2.1) as assessed by investigator. Objective response rate (ORR) is the proportion of participants in the analysis population with objective response.

- Duration of Response (DOR)

For participants who demonstrate an objective response as assessed by investigator, per disease-specific criteria, duration of response is defined as the time from the first documented evidence of an objective response until disease progression or death due to any cause, whichever occurs first.

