## **9.6 Statistical Methods**

This section describes the statistical methods that address the primary and secondary objectives. Analysis by dose level will be performed by the initially assigned dose level. Methods related to exploratory endpoints will be described in the sSAP.

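### The supplementary ORR pooled over everyone who ends up on 65 mg does not estimate response to 65 mg, because a 45 mg starter's entry depends on later events and responses are not tied to the dose being taken

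*Combined protocol and SAP*

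**What the plan says.** The main rule, in Section 9.6, is "Analysis by dose level will be performed by the initially assigned dose level". Section 9.5.2 and Table 11 set the efficacy population as all participants as treated. Section 9.6.2 gives response rates with an exact 95% Clopper-Pearson interval, counts missing data as non-response, and then adds: "This analysis will also be performed based on data pooled across all participants who eventually receive 65 mg". Section 9.5 does not define this pooled set, and neither the Section 9.1 summary nor Table 11 lists it.

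Four other provisions decide who is in the set and what counts:

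- **Response (Section 9.4.2):** "OR is defined as participants who achieve at least a PR, per disease-specific criteria". There is no condition on the dose being taken when the response occurs.
- **Earliest escalation (Section 4.1):** "In or after cycle 4, participants receiving 45 mg of nemtabrutinib may be escalated to the 65 mg". Tolerability of 65 mg must be confirmed first, and the decision is made "at the discretion of the investigator after discussion with the participant, upon the consultation with sponsor" (Section 6.6).
- **Start of the higher dose (Section 6.6):** "the higher dose can be utilized from the Day 1 of next cycle based on the approved date".
- **First assessment (Section 8.2.2):** "The first on-study imaging assessment and tumor response assessment should be performed at 12 weeks", with a window of 7 days either side, counted from Cycle 1 Day 1.

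Section 4.1 continues treatment until progression, unacceptable toxicity or another stopping criterion. Section 7.1 makes discontinuation permanent.

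**The concern.** Two separate problems follow from defining the set by what participants eventually receive.

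**Selection on a post-baseline event.** A 45 mg starter who stops before escalating can never enter. In the all-treated analysis that participant is a non-responder; in the pooled analysis the participant is absent. Everyone who starts on 65 mg counts from the first dose, early failures included. The two parts of the pooled set are therefore chosen by different rules, and the Clopper-Pearson interval treats the result as a simple binomial sample.

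**Responses not tied to dose.** A partial response reached on 45 mg counts in the pooled rate once the participant takes a 65 mg dose, even if nothing changes afterwards.

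At stake is how a secondary endpoint will be read. The plan names 65 mg as the recommended Phase 2 dose, and when anyone escalates this figure has a larger 65 mg denominator than the assigned-dose ORR. It could easily be quoted as the response rate at that dose.

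**Working it through.** **1. Method check.** The documents give no figure for the pooled ORR. The Clopper-Pearson method reproduces the 65 mg CLL/SLL result quoted from BELLWAVE-001 in Section 2.2.2.3: 32/57 = 56.1% (42.4, 69.3). Excluding partial response with lymphocytosis, as this trial's secondary endpoint does, the quoted rate is 29.8% (17/57).

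**2. Timing, in days after Cycle 1 Day 1.** Cycles are 28 days (Section 6.1.1).

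- First assessment: 84 ±7, so 77 to 91.
- Cycle 4 Day 1: 3 × 28 = 84, with a ±3-day visit window.
- Cycle 5 Day 1, if approval comes during Cycle 4: 4 × 28 = 112.

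The earliest 65 mg dose and the first assessment share the same nominal date. A response at that assessment is normally a 45 mg response. The exception is a scan late in its window after a Cycle 4 Day 1 escalation, which follows at most 91 − 81 = 10 days of 65 mg if that visit was 3 days early. If escalation starts at Cycle 5, there is no exception.

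**3. Expected pooled ORR when dose has no effect.** Assume 6 participants per level, response rate p at both doses, a share q of 45 mg starters not escalated, all 45 mg responders escalated, and no new responses after escalation.

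Pooled ORR = (6p + 6p) / (6 + 6(1 − q)) = 12p / (12 − 6q)

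For p = 29.8% the numerator is 12 × 0.298 = 3.576.

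| 45 mg starters escalated | q | Denominator | Pooled ORR |
|---|---|---|---|
| 6 of 6 | 0 | 12 | 29.8% |
| 5 of 6 | 1/6 | 11 | 32.5% |
| 4 of 6 | 1/3 | 10 | 35.8% |
| 3 of 6 | 1/2 | 9 | 39.7% |

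Over the same range of q, p = 20% gives 20.0% to 26.7%, and p = 40% gives 40.0% to 53.3%.

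**4. Opposite selection.** If 3 non-responders escalate and all 45 mg responders stay on 45 mg, the pooled ORR is 6 × 0.298 / (6 + 3) = 1.788/9 = 19.9%.

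**5. Unequal rates.** Section 4.3 reports an ORR that rises with dose. Taking 20% at 45 mg (assumed) and 29.8% at 65 mg, the numerator is 6 × 0.20 + 6 × 0.298 = 2.988. The pooled ORR is 2.988/12 = 24.9% if all escalate and 2.988/9 = 33.2% if half do. It falls on either side of 29.8%.

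**6. Whole-participant example (assumed counts).** At 65 mg, 2 of 6 respond. At 45 mg, 2 respond at Week 12 and then escalate, 2 escalate with stable disease and never respond, and 2 progress before Cycle 4.

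| Analysis | Result (95% CI) |
|---|---|
| Pooled, as written | 4/10 = 40.0% (12.2, 73.8) |
| Initially assigned 65 mg | 2/6 = 33.3% (4.3, 77.7) |
| All treated | 4/12 = 33.3% (9.9, 65.1) |
| Pooled set, counting only responses first documented on 65 mg | 2/10 = 20.0% (2.5, 55.6) |

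The last row matters for the fix: it turns the two 45 mg responders into failures and is biased downward.

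**The case against.** The strongest reply is that the sound estimate is already planned. Section 9.6 analyses by initially assigned dose, the pooled analysis is introduced only as an addition, and its description is open about mixed exposure. No hypothesis is tested. Dose finding runs on DLT counts, the 65 mg recommended dose came from other studies, and no rule uses the pooled ORR. With 6 to 12 participants, imprecision far exceeds the shift, as the intervals above show. If nobody escalates, the set equals the 65 mg cohort and the problem disappears.

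All of this stands, and it limits the weight of the point. It does not cure the defect: no section says which responses count or keeps non-escalated 45 mg starters in view. Section 9.6.2 defers details of duration of response to the supplemental SAP, but not those of objective response.

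A reader might also infer that every first-scan response in an escalated participant arose entirely on 45 mg. The assessment and visit windows do not support that; normally is as far as the text goes.

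**Conclusion.** The concern holds for the supplementary analysis. Membership depends on remaining on treatment and being selected, and counted responses are not tied to 65 mg, so the pooled rate does not estimate response to 65 mg. In the equal-rate illustration with all 45 mg responders escalated, the expected value runs from 29.8% to 39.7% as the escalated share falls from all to half. It can be lower if mainly non-responders escalate. The 29.8% is a CLL/SLL rate at 65 mg, applied here to mixed histologies and to 45 mg; that, the escalated shares and the counts are assumptions.

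Three stronger readings are tempting and not supported:

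- **The trial lacks a proper 65 mg ORR.** It has one, by initially assigned dose.
- **The bias is always upward.** Escalation is discretionary, so the direction is not fixed.
- **The plan would report anything from about 20% to 45% when the truth is 30%.** That range joins opposite extremes: only non-responders escalated (19.9%), and all responders escalated with 6 starters at 45 mg, 3 at 65 mg and half escalated (9 × 0.298 / 6 = 44.7%).

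This is worth correcting, but neither the primary safety results nor any decision in the protocol depends on it.

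**What to change.** In Section 9.6.2, state that the 65 mg ORR is the one for participants initially assigned 65 mg, and remove the pooled rate with its Clopper-Pearson interval. Put a descriptive table in its place:

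- For each escalated 45 mg starter: best response before the first 65 mg dose, and any new or deepened response after it, both judged against the pre-treatment baseline used in Appendix 9.
- For each 45 mg starter who did not escalate: the reason and the response status.

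Do not keep a pooled denominator in which participants who responded before escalation count as non-responders; that exchanges one bias for another. Resetting the baseline at escalation would depart from the Appendix 9 criteria.

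The drafting is a sentence or two and one small table. The costs are that the 65 mg ORR rests on 3 to 6 participants and that the opening of Section 9 requires a protocol amendment for changes to methods serving secondary objectives.

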### 9.6.3 Statistical Methods for Pharmacokinetic Analysis

Plasma concentrations of nemtabrutinib will be summarized by planned visit and time for each dose level separately. PK parameters will be summarized by dose level. Details of statistical analysis of pharmacokinetic analyses will be documented in the sSAP as appropriate.

#### 9.6.4 Demographic and Baseline Characteristics

Demographic variables, baseline characteristics, primary and secondary diagnoses, and prior and concomitant therapies will be summarized in the population which consists of all allocated participants. The number and percentage of participants screened and randomized and the primary reasons for screening failure and discontinuation will be displayed.

#### 9.7 Interim Analyses

No interim analysis will be performed. Data will be examined on a continuous basis to allow for dose finding decisions.

#### 9.8 Multiplicity

There will be no multiplicity control in this study since no hypothesis testing is planned.

#### 9.9 Sample Size and Power Calculations

Each dose level assessed will have a minimum of 3 participants. Based on the occurrence of DLTs, up to 6 participants may enroll per dose level. The actual sample size is dependent on the number of dose levels tested and emerging safety data. The estimated DLT rate among 3 or 6 participants in the DLT evaluable population and the 90% Bayesian credible interval based on a prior distribution of Beta (1,1) are provided in [Table 12](#).

Table 12 Precision of the Estimated DLT Rates

Number of DLT events	N=3		N=6	
	DLT rate	90% credible interval	DLT rate	90% credible interval
0	0.000	(0.013, 0.527)	0.000	(0.007, 0.348)
1	0.333	(0.098, 0.751)	0.167	(0.053, 0.521)
2	0.667	(0.249, 0.902)	0.333	(0.129, 0.659)
3	1.000	(0.473, 0.987)	0.500	(0.225, 0.775)
4	NA	NA	0.667	(0.341, 0.871)
5	NA	NA	0.833	(0.479, 0.947)
6	NA	NA	1.000	(0.652, 0.993)

#### 9.10 Subgroup Analyses

No subgroup analyses will be performed.

#### 9.11 Compliance (Medication Adherence)

Drug accountability data for study intervention will be collected during the study. Any deviation from protocol-directed administration will be reported.

## **9.12 Extent of Exposure**

The extent of exposure will be summarized as duration of treatment in days.

## **10 SUPPORTING DOCUMENTATION AND OPERATIONAL CONSIDERATIONS**

### **10.1 Appendix 1: Regulatory, Ethical, and Study Oversight Considerations**

#### **10.1.1 Code of Conduct for Clinical Trials**

##### **Merck Sharp & Dohme LLC, Rahway, NJ, USA (MSD)**

#### **I. Introduction**

##### **A. Purpose**

Merck Sharp & Dohme LLC, Rahway, NJ, USA (MSD), through its subsidiaries, conducts clinical trials worldwide to evaluate the safety and effectiveness of our products. As such, we are committed to conducting these trials in compliance with the highest ethical and scientific standards. Trial conduct includes processes from design to reporting, including planning, initiating, performing, recording, oversight, evaluation, analysis and reporting activities as appropriate. Protection of participants in clinical trials is the overriding concern in the design and conduct of clinical trials. In all cases, MSD clinical trials will be conducted in compliance with MSD's global standards, local and/or national regulations (including all applicable data protection laws and regulations), Regulation (EU) 536/2014, the International Council for Harmonisation Good Clinical Practice (ICH GCP) E6 and ICH General Considerations for Clinical Studies E8, and in accordance with the ethical principles that have their origin in the Declaration of Helsinki.

##### **B. Scope**

Highest ethical and scientific standards shall be endorsed for all clinical interventional investigations sponsored by MSD irrespective of the party (parties) employed for their execution (e.g., contract research organizations, collaborative research efforts). This Code is not intended to apply to trials that are observational in nature, or which are retrospective. Further, this Code does not apply to investigator-initiated trials, which are not under the full control of MSD.

#### **II. Scientific Issues**

##### **A. Trial Conduct**

##### **1. Trial Design**

Except for pilot or estimation trials, clinical trial protocols will be hypothesis-driven to assess safety, efficacy, and/or pharmacokinetic or pharmacodynamic indices of MSD or comparator products. Alternatively, MSD may conduct outcomes research trials, trials to assess or validate various endpoint measures, or trials to determine patient preferences, etc.

The design (i.e., participant population, duration, statistical power, randomization, and blinding) must be adequate to address the specific purpose of the trial and shall respect the data protection rights of all participants, trial site staff and, where applicable, third parties. Input may be considered from a broad range of

stakeholders, including patient advocacy groups/patients representing the trial population, caregivers, and healthcare providers to ensure operational feasibility. The use of innovative digital health technologies will be considered. Factors critical to the quality of the trial should also be identified. These factors are attributes of a trial that are fundamental to the protection of participants, the reliability and interpretability of the trial results and the decisions made based on those trial results. Risks to critical to quality factors should be managed prospectively and adjusted when new or unanticipated issues arise once the trial has begun. All trial protocols are and will be assessed for the need and capability to enroll underrepresented groups. Participants must meet protocol entry criteria to be enrolled in the trial.

## **2. Site Selection**

MSD's clinical trials are conducted globally in many different countries and in diverse populations, including people of varying age, race, ethnicity, gender, and accounting for other potential disease related factors. MSD selects investigative sites based on medical expertise, access to appropriate participants, adequacy of facilities and staff, previous performance in clinical trials, as well as budgetary considerations. Prior to trial initiation, sites are evaluated by MSD personnel (or individuals acting on behalf of MSD) to assess the ability to successfully conduct the trial. Individuals involved in trial conduct receive training commensurate with their role prior to their becoming involved in the trial.

Where appropriate, and in accordance with regulatory authority guidance, MSD will make concerted efforts to raise awareness of clinical trial opportunities in various communities. MSD will seek to engage underrepresented groups and those disproportionately impacted by the disease under study. MSD will support clinical trial investigators to enroll underrepresented groups and expand access to those who will ultimately use the products under investigation.

